8.1.9 Accountability

The investigator, or a responsible party designated by the investigator, should maintain a careful record of the inventory and disposition of the agent using the NCI Drug Accountability Record Form (DARF) or another comparable drug accountability form. (See the NCI Investigator's Handbook for Procedures for Drug Accountability and Storage.)

8.1.10 Destruction and Return

At the end of the study, unused supplies of neratinib should be destroyed according to institutional policies. Destruction will be documented in the Drug Accountability Record Form.

8.2 Fulvestrant

8.2.1 Description

Fulvestrant injection for intramuscular administration is an estrogen receptor antagonist. The chemical name is 7-alpha-[9-(4,4,5,5,5-penta fluoropentylsulphonyl) nonyl]estra-1,3,5-(10)- triene-3,17 beta-diol. The molecular formula is C₃₂H₄₇F₅O₃S and its structural formula is: OH OH (CH₂)₉SO(CH₂)₃CF₂CF₃. Fulvestrant is a white powder with a molecular weight of 606.77. The solution for injection is a clear, colorless to yellow, viscous liquid.

Fulvestrant is commercially available and considered standard-of-care for patients with hormone receptor positive, metastatic breast cancer. The dose, schedule, and mode of administration used in this trial are identical to the dose, schedule, and mode of administration approved for use for this indication by the U.S. FDA.

Fulvestrant will be charged to the patient and/or insurance company as it is considered standard-of-care.

8.2.2 Form

Fulvestrant injection is commercially available as a sterile, single patient, prefilled syringe containing 250 mg at a concentration of 50 mg/mL. The solution is a clear, colorless to yellow, viscous liquid. In addition to the fulvestrant, each injection contains as inactive ingredients alcohol, USP, benzyl alcohol, NF, and benzyl benzoate, USP, as co-solvents and castor oil, USP, as a co-solvent and release rate modifier.

8.2.3 Storage and Stability

Syringes of fulvestrant should be stored in the original container and refrigerated at 2-8°C.

8.2.4 Handling

Fulvestrant requires no specific handling precautions. Qualified personnel, familiar with procedures that minimize undue exposure to themselves and the environment, should undertake the preparation, handling, and safe disposal of the chemotherapeutic agent in a self-contained and protective environment.

8.2.5 Preparation

Remove syringe from tray and check that it is not damaged. Peel open the safety needle outer packaging. Break the seal of the white plastic cover on the syringe luer connector to remove the cover with the attached rubber tip cap. Twist to lock the needle to the luer lock connector. Remove needle sheath. Remove excess air from the syringe (a small bubble may remain).

8.2.6 Administration

Fulvestrant will be administered at a dose of 500 mg (2 x 250 mg injections) IM on Cycle 1 Day 1, Cycle 1 Day 15, Cycle 2 Day 1, and on Day 1 of each subsequent cycle. Cycle length = 28 days.

Fulvestrant will be administered slowly into each buttock. Immediately upon withdrawal of syringe from patient activate needle protection device by pushing lever arm forward until needle tip is fully covered. Visually confirm that the needle arm has advanced and that the needle tip is fully covered. If unable to activate, discard immediately into an

approved sharps container.

8.2.7 Ordering

Fulvestrant is commercially available and will be ordered by each prescribing provider for the duration for the study.

8.2.8 Accountability

Fulvestrant is commercially available and therefore accountability should be performed as standard policy in the investigational site.

8.2.9 Destruction

Fulvestrant is commercially available and therefore destruction should be performed as standard policy in the investigational site.

9. BIOMARKER, CORRELATIVE, AND SPECIAL STUDIES

Table 6: Specimen Collection Schedule

Specimen	Screening	Cycle 1		Subsequent Cycles	End of treatment/ Progression	Shipping Condition	Ship to
		Day 1 (± 1 Day)	Day 15	Day 1 (± 3 Days)			
ctDNA Collection (Section 9.1)		x	x	x	x	Ambient	DF/HCC Core Blood and Tissue Bank
Archival tumor tissue (blocks or slides) ^a (Section 9.2)	x					Ambient	DFCI BOC study team
Required Fresh tumor tissue biopsy ^b (Section 9.3)	x	x				Frozen in OCT	DF/HCC Core Blood and Tissue Bank
Optional Fresh tumor tissue biopsy (Section 9.3)					x	Frozen in OCT	DF/HCC Core Blood and Tissue Bank

- a. If archival tumor tissue is not available, fresh tissue biopsy must be performed prior to treatment start. Biopsy may be done as part of screening or on C1D1 before treatment begins. **For external site patients**, biopsy should be done after registration or on C1D1 prior to treatment start. See section 9.3 below.
- b. Fresh tumor biopsy of accessible metastatic lesion is mandatory before treatment begins. The biopsy may be performed at screening or on Cycle 1 Day 1 prior to dosing. **For external site patients**, biopsy should be done after registration or on C1D1 prior to treatment start. See section 9.3 below.

9.1 ctDNA Collection

9.1.1 Collection of Blood Specimen(s)

For ctDNA analyses, two 10 mL blood samples will be drawn into two Streck Tubes. Streck Tubes will be supplied to sites. Blood will be collected at:

- Cycle 1 Day 1 (prior to treatment start)
- Cycle 1 Day 15
- Subsequent Cycles Day 1
- End of Treatment

Every effort will be made to coordinate study blood draws with clinically-indicated blood tests to minimize additional venipuncture. Research coordinators will track participants closely and make every effort to collect blood at required timepoints. Some blood draws

will be missed or fall outside timeframe window due to the following circumstances and will not be considered deviations from the protocol:

- Unanticipated changes in treatment regimens and last minute clinic visits,
- The serial ctDNA blood draws may not occur as scheduled, depending on the participant's clinical schedule and visits at their participating institution. We do not plan to bring participants back to clinic solely for the purpose of a research blood draw and will make every attempt to coordinate it with a clinically indicated blood draw. Missed ctDNA draws due to these reasons will not be considered deviations or violations.

It is anticipated that future studies will include evaluation of genetic, immunologic, hormonal, and/or other issues related to breast cancer. We will inform participants in the informed consent document that we will use their specimens for research related to breast cancer and other cancers. If investigators wish to obtain identifiable information as part of their biomarker research, they will be required to submit such plans for IRB approval.

9.1.2 Handling of Blood Specimens(s)

Blood will be processed and banked in the DF/HCC Core Blood and Tissue Bank for future research purposes or until sent to the Broad Institute for sequencing.

Blood collected in Streck tubes at non-DFCI sites is to be shipped to DFCI within 24 hours of collection as per instructions below. Upon receipt at DFCI, Streck Tubes will be kept at room temperature and processed within 7 days.

Tube precautions:

- Fill the Streck tube completely and immediately mix by gentle inversion 8 to 10 times. Inadequate or delayed mixing may result in inaccurate results.
- If samples cannot be shipped within 24 hours of collection, contact DFCI. DO NOT FREEZE OR REFRIGERATE TUBES as this could cause issues with sample integrity.
- Do not use tubes after expiration date.
- Fill the tube completely.

9.1.3 Shipping of Blood Specimen(s)

Complete a Specimen Requisition Form (Appendix F) to be sent with the tubes; make a copy of the requisition for the participant's research chart prior to sending.

Ship Monday through Thursday within 24 hours of collection at ambient temperature overnight to:

Brigham and Women's Hospital
DF/HCC Core Blood and Tissue Bank
[name]
[name]
[name]

DO NOT FREEZE OR REFRIGERATE STRECK TUBES. Streck tubes must be stored at room temperature to preserve the sample.

If blood specimens must be collected on Friday, the specimens should be stored over the weekend and shipped on Monday. When storing tubes over a weekend, Streck tubes should be stored at room temperature until shipment.

Email the assigned study coordinator and [REDACTED] with the sample information and tracking information the day before shipping specimens. Please include UPS or FedEx tracking information for the sample.

9.2 Archival Tissue

9.2.1 Collection of Archival Tissue Specimen(s)

Archival tissue (either paraffin blocks or unstained slides) will be collected for molecular characterization including potential resistance mechanisms, predictive biomarkers, and immunological function. Tumor (breast and/or lymph node) tissue from the initial breast cancer surgery is preferred. For participants diagnosed with de novo metastatic disease then tissue from the initial diagnostic biopsy should be collected. Additionally, available archival tissue from surgery or biopsy for metastatic disease will be collected.

This material should be provided preferably as paraffin blocks, if not, at least ten 5micron sections on charged or coated slides and ten 5-7 micron sections on regular non-coated slides should be submitted (20 slides total with 10 from primary and 10 from metastatic sites). For those patients that do not undergo a baseline biopsy, 20 slides from the metastatic site and 10 slides from the primary should be submitted (30 slides total).

Tissue needs to be located and availability must be confirmed at the time of registration, as indicated in eligibility criterion 3.1.4. If archival tissue is not available, patients will be required to undergo a tumor biopsy prior to treatment start. This biopsy can be done during screening or on C1D1 before treatment begins. **For external site participants,** biopsy should be performed after registration or on C1D1 prior to dosing. Details for this biopsy including collection, processing, and shipping are outlined below in Section 9.3.

Patients will not be able to start study drugs without confirmation of tissue availability or biopsy. Tissue needs to be submitted to DFCI within 3 weeks of study initiation (treatment start).

9.2.2 Handling of Archival Tissue Specimens(s)

Label all blocks or slides with the participants Study ID number, Initials, Date of Birth and surgical site (site of disease from which sample was obtained). Include a copy of the associated de-identified pathology report labeled with the participant's Study ID number, Initials, and Date of Birth with blocks/slides.

9.2.3 Shipping of Archival Tissue Specimen(s)

Include a copy of the Specimen Requisition Form (Appendix F) with your shipment. Keep a copy of the requisition in the participant's research chart. Tissue needs to be submitted to DFCI within 3 weeks of study initiation (treatment start).

Ship at ambient temperature to the DFCI study team:

Dana Farber Cancer Institute
Breast Oncology
[name]
[name]

Email the assigned study coordinator with the sample and tracking information the day before shipment. Blocks will be returned to sites after the completion of the specimen analysis. Please include UPS or FedEx tracking information for the sample.

9.3 Fresh Tissue Biopsy Collection

9.3.1 Collection of Pre-treatment Biopsy Specimen(s)

Participants will undergo a required research biopsy of a reasonably accessible metastatic lesion (chest wall, skin, subcutaneous tissue, lymph nodes, skin, breast, bones, lung, and liver metastases) before treatment begins. The biopsy may occur during screening or on Cycle 1 Day 1 before treatment begins. **For external site participants**, biopsy should be performed after registration or on C1D1 prior to dosing. If the biopsy is done prior to registration, please store the sample in a -80°C freezer until the time of shipment (once the participant is registered). If a reasonably accessible metastatic lesion is not available, the patient may go on study provided that archived tissue is available. However, if a reasonably accessible site is available for biopsy, the patient must agree to biopsy. Any patients not undergoing biopsy must be approved for study enrollment by the Overall Principal Investigator at DFCI.

Biopsies may be done with local anesthesia or intravenous conscious sedation, according to institutional guidelines. If a biopsy requires general anesthesia, then it is only allowed if acquisition of tissue is clinically indicated, and excess tissue may be collected for research purposes. Patients without sites available for biopsy must have available tissue [archived formalin-fixed paraffin embedded blocks (FFPB), blocks from which slides can be created, or fresh frozen tissue from original diagnosis or metastatic setting] for correlative studies. Tissue needs to be located and available at the time of registration. Tissue specimens will be collected from tumor lesions using standard institutional procedures.

9.3.2 Collection of Post-Progression Biopsy Specimen(s)

Patients will be asked at the time of consent if they would like to provide an optional biopsy at the time of progression. If patients agree to participate in the optional progression biopsy at the time of consent, they may refuse at the time of progression if they wish, without resulting in a deviation or violation. This tissue will be used for molecular characterization including potential resistance mechanisms, predictive biomarkers, and immunological function.

Tissue specimens will be collected from tumor lesions using standard institutional procedures.

9.3.3 Tissue Biopsy Guidelines

- **The cost of the biopsies will be covered by the study if they are being done for research only.** However, it is recognized that biopsies might be considered to aid in clinical management (for example, to re-assess ER, PR, and HER2 status). In the case of a clinically indicated biopsy (with an additional “research pass”), the cost of the biopsy will be charged to the patient and/or her insurance company.
- Patients who undergo an attempted research biopsy procedure for the purpose of this protocol, and in whom inadequate tissue is obtained, are not required to undergo a repeat biopsy in order to continue on protocol.

The amount of tissue collected will follow the guidelines listed below. If a patient has more than one site of disease, only one site needs to be biopsied, and the site is left to the discretion of the patient and her treating physician. Core biopsies are preferred; punch biopsies may be done when necessary, but fine needle aspirates are not allowed.

Breast:

- A goal of 3-6 core biopsy will be obtained using standard institutional guidelines for a diagnostic core biopsy of a breast mass

Skin/Chest wall:

- A goal of two 5-mm punch biopsies will be obtained

Lymph node/Soft tissue:

- A goal of 3-6 core biopsy specimens will be obtained using an 18-gauge needle.

Liver:

- A goal of 3-6 core biopsy specimens will be obtained using an 18-gauge needle.

Lung:

- Because of the risk of pneumothorax associated with core needle biopsies of lung nodules, no core biopsies of lung nodules will be performed on this protocol; unless if they are clinically indicated.

Bone:

- Because the yield of malignant tissue from bone biopsies tends to be relatively low, if a patient has another accessible site of disease (e.g., skin, lymph node, liver), that site should be biopsied preferentially. If bone is the only biopsy-accessible site, then a goal of 1-3 core biopsy specimens will be obtained using an 11 to 13-gauge needle.

Please note that the above are guidelines for the amount of tissue to be obtained and are not meant to replace clinical judgment at the time the procedure is performed. Less than the goal quantity of tissue is accepted for each type of biopsy, and will be left to the clinical judgment of the physician performing the procedure. If ascites or pleural fluid is to be used as the investigational biopsy specimen, consideration should be given to confirming the malignant nature of the ascites or pleural fluid prior to study entry.

In order to minimize the risk of a biopsy, only qualified personnel will perform these procedures. Prior to the procedure, the physician performing the procedure will discuss the risks with each study participant, answer any questions, and obtain a separate procedure consent. Patients will be evaluated for co-morbidities or concomitant medications that may increase the risk of potential complications. For biopsies of lesions that are not superficial and clearly palpable, imaging studies such as CT or ultrasound will be used to guide the biopsy in order to minimize the risk of damage to adjacent structures. After lymph node biopsies, patients will be observed a minimum of 2 hours (range 2-4 hours) after the procedure, or according to standard institutional guidelines. After liver biopsies, patients will be observed a minimum of 4 hours (range 4-6 hours) after the procedure, or according to standard institutional guidelines. Less than the goal quantity of tissue is accepted for each type of biopsy, and will be left to the clinical judgment of the physician performing the procedure.

9.3.4 Handling of Fresh Tissue Biopsy Specimens(s)

Following the biopsy of a specimen, all tissue cores will be snap-frozen in OCT compound intra-operatively. After the biopsy is performed, the tissue mass is placed on a dry sterile gauze and the tumor tissue is separated using forceps. Two pieces (cores) of tumor tissue are placed on a pre-frozen bed of OCT in each cassette, typically ending up with 3 cassettes per biopsy (the last cassette will contain many small pieces of tumor tissue). Cassettes are then filled with OCT, completely covering the tissue and limiting the amount of bubbles (forceps can be used to pop any bubbles). Tissue must be frozen immediately by placing cassettes on dry ice in a biohazard cooler; freezing of samples in OCT with dry ice takes about 10 minutes freezing time. Once samples are frozen, place in plastic bag; label bag with date, protocol number, patient number, patient initials, and number of biopsy samples included. Store in -80°C freezer until the time of shipment.

All samples will be anonymized by assigning a unique sample ID number prior to use. Tissue biopsy collection and processing materials are not provided by the study. Coded laboratory specimens will be stored in the Tumor Bank of the DF/HCC. These specimens will become the property of DF/HCC. In cases where the research sample is forfeited for clinical purposes, this sample will be flagged in spreadsheet to indicate it can be used for research purposes if there is any left over after clinical use.

9.3.5 Shipping of Biopsy Specimen(s)

Complete the Specimen Requisition Form (Appendix F) to be sent with the biopsy samples. Make a copy of the requisition for the participant's research chart prior to sending.

Ship biopsy samples overnight Monday – Thursday to:

Email the assigned study coordinator and [redacted] with the sample information and tracking information the day before shipping specimens. Please include UPS or FedEx tracking information for the sample.

10. STUDY CALENDAR

Baseline evaluations are to be conducted within 4 weeks prior to registration. Scans and x-rays must be done ≤ 4 weeks prior to registration. MUGA or echo must be done within 60 days prior to registration. In the event that the participant's condition is deteriorating, laboratory evaluations should be repeated within 48 hours prior to initiation of the next cycle of therapy.

Assessments must be performed prior to administration of any study agent. Study assessments and agents should be administered within ± 3 days of the protocol-specified date, unless otherwise noted. ECHO/MUGA assessments should be performed within 7 days of the protocol-specified date; scans performed ± 7 days from the protocol-specified date. Subjects who discontinue study therapy but have responsive or stable disease will be followed approximately every 3-6 months for progression and overall survival. Minor deviations in scheduling of procedures (i.e. cycle 1 procedures, ± 3 days; from cycle 2 forward treatment schedule, -3 days to +7 days; from Cycle 3 forward, ± 7 days) are allowed to accommodate for vacation, holidays, or patient convenience.

Table 7: Study Calendar

	Baseline	Cycle 1			Subsequent Cycles			End of therapy or Progression	Follow up (every 6 months)
	≤ 4 Weeks prior to registration	Day 1	Day 2, 3, 4 (In person or by phone)	D15	Day 1	Every 2 cycles	Every 3 cycles		
Informed consent	X								
Patient Education for Diarrhea	X	X							
Demographics	X								
Medical/surgical history	X								
Concomitant medications (See Section 5.4)	X	X			X			X	
Height	X								
Vital Signs (Weight, Blood Pressure)	X	X		X	X				
Physical examination, ECOG PS	X	X			X			X	
12-lead EKG	X								
MUGA or echocardiogram ^A	X						X		
Urine Pregnancy test	X								
Urinalysis	X								
CBC, including differential and platelets ^B	X	X			X			X ^F	
Serum chemistries ^B	X	X			X				
Research Collection: Blood or Tissue ^C	X ^C	X		X	X			X	
Tumor Evaluation (MRI or CT and clinical assessment of visible of palpable lesions) ^D	X					X			
Bone scan ^E	X					X			
Adverse event evaluation		X	X		X			X	
Phone call to assess for diarrhea (See Sections 5.3.3.)			X						
Phone call for survival assessment and subsequent therapies (See Section 5.6)									X

- A. Baseline MUGA or ECHO within 60 Days prior to registration. It is strongly recommended to use the same method of cardiac evaluation at each time point. ECHO/MUGA assessment will be completed at the end of every 3 cycles and should be completed within 7 days of the subsequent cycle. If ECHO/MUGA completed on Day 1 of the applicable cycle, a preliminary read of the test will be needed before the patient can be dosed on Day 2 of the cycle. If a preliminary read is not available, the patient should be told to hold neratinib until the result becomes available.
- B. Hematology: PTT and PT/INR drawn at baseline for all patients and at end of therapy/progression for patients who undergo the optional biopsy. Chemistries: Sodium, potassium, chloride, bicarbonate, BUN, creatinine, total protein, albumin, total bilirubin, SGOT(AST), SGPT(ALT), Alkaline Phosphatase
- C. See Section 9.
- D. Patients should have imaging of the Chest-Abdomen-Pelvis at baseline. After completion of 12 cycles, scans can decrease in frequency to every 3 cycles. If there are no pelvic lesions or abnormalities identified, future imaging may include chest and abdomen only, as appropriate. For alternative imaging options (non-CT), please see 11.1.3. Window around imaging is +/- 7 days.
- E. Bone scan not required for study but may be done at baseline and every 2 cycles (+/- 7 days), if clinically indicated.
- F. PTT and PT/INR only, for patients who undergo the optional biopsy

11. MEASUREMENT OF EFFECT

11.1 Antitumor Effect – Solid Tumors

For the purposes of this study, participants should be re-evaluated for response every 2 cycles (or 8 weeks). After completion of 12 cycles, scans can decrease in frequency to every 3 cycles. In addition to a baseline scan, confirmatory scans should also be obtained 4 weeks following initial documentation of objective response.

Response and progression will be evaluated in this study using the new international criteria proposed by the Response Evaluation Criteria in Solid Tumors (RECIST) guideline (version 1.1) [*Eur J Ca* 45:228-247, 2009]. Changes in the largest diameter (unidimensional measurement) of the tumor lesions and the shortest diameter in the case of malignant lymph nodes are used in the RECIST criteria.

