4.3 General Guidelines for Other Investigative Sites

Eligible participants will be entered on study centrally at the Coordinating Center through the Study Coordinator or Project Manager. The list of required forms can be found in Section 4.4.

It is recommended that participants begin protocol treatment within 7 business days, and no more than 30 days from registration. Issues that would cause treatment delays should be discussed with the Overall PI. If a participant does not receive protocol therapy following registration, the participant's registration on the study must be canceled. The Study Coordinator should be notified of cancellations as soon as possible.

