11.1.6 Progression-Free Survival

Overall Survival: Overall Survival (OS) is defined as the time from randomization (or registration) to death due to any cause, or censored at date last known alive.

Progression-Free Survival: Progression-Free Survival (PFS) is defined as the time from randomization (or registration) to the earlier of progression or death due to any cause. Participants alive without disease progression are censored at date of last disease evaluation.

Time to Progression: Time to Progression (TTP) is defined as the time from randomization (or registration) to progression, or censored at date of last disease evaluation for those without progression reported.

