13. STATISTICAL CONSIDERATIONS

13.1 Study Design/Endpoints

This is a randomized two-arm phase II study of neratinib +/- fulvestrant in patients with metastatic ER+/HER2+ breast cancer. The primary objective is to compare the progression-free survival between neratinib monotherapy versus neratinib plus fulvestrant. The endpoint is progression-free survival (PFS) defined as the interval from the date of randomization to progression or death. Patients who are alive and progression-free will be censored at the date of last disease assessment. Randomization will be 1:1 within stratum defined by the number of prior lines of therapy (≤ 3 versus ≥ 4) and prior use of fulvestrant (yes or no). Prior to Version 2 of the protocol, participants were stratified by the number of prior lines of therapy (≤ 3 versus ≥ 4) and PR expression (0-10% vs. 11% or more).

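### PFS is timed from randomization but tumour scans are counted in treatment cycles; anchoring scans to randomization would close off a possible, though not demonstrated, bias in the primary comparison

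*Combined protocol and SAP*

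**What the plan says.** **Time origin.** Section 13.1 has PFS "defined as the interval from the date of randomization to progression or death". Section 11.1.6 is looser: PFS is "defined as the time from randomization (or registration) to the earlier of progression or death due to any cause".

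**Scan clock.** Section 11.1 states that "participants should be re-evaluated for response every 2 cycles (or 8 weeks" apart, and Table 7 lists tumour evaluation under a column for every two cycles. Section 5.1 makes a cycle 28 consecutive days of treatment. No section ties a scan to the randomization date. The 8-week equivalence gives an interval, not an origin. Section 10 allows scans ±7 days and lets schedules move: "from cycle 2 forward treatment schedule, -3 days to +7 days; from Cycle 3 forward, ± 7 days". Footnote D adds: "After completion of 12 cycles, scans can decrease in frequency to every 3 cycles".

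**Gap between the two clocks.** Section 4.3, which covers sites outside DF/HCC, recommends that participants "begin protocol treatment within 7 business days, and no more than 30 days from registration". Section 4.1 sets no explicit limit for DF/HCC sites. Section 11.1.3 constrains the gap indirectly at every site, because baseline evaluations may not be older than 4 weeks when treatment starts.

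**Arm-specific features.** Neratinib is supplied for the study. Fulvestrant, in Arm A only, is a commercial product: "Fulvestrant will be charged to the patient and/or insurance company as it is considered standard-of-care". Section 6.2 allows fulvestrant to be held for up to 28 days and does not say whether the cycle clock moves. Section 6.1 does say so for neratinib: cycles stay on schedule during a hold. No blinding or placebo injection is described.

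**The concern.** Progression is mostly dated at a scan. If one arm starts treatment later after randomization, or its cycles stretch, its scans fall later on the PFS clock. Events in that arm then tend to be recorded just after the matching cluster of events in the other arm. The logrank test depends on the order of event times, so a difference of a few days can look like a treatment effect although the tumours behave identically. At stake is the one-sided 0.10 error rate of the primary comparison or, if Arm B were the later arm, its power. The plan specifies no sensitivity analysis for assessment timing that would reveal the problem.

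**Working it through.** **1. The plan's own figure.** Inputs from Section 13.2: 125 events, medians 4 and 6 months (HR 4/6), one-sided alpha 0.1, futility stop if Z < 0 at 63 events. Without the futility look, power = Φ(√125/2 × ln 1.5 − 1.2816) = Φ(2.267 − 1.282) = 83.8%. Adding the futility stop through a bivariate normal gives 82.3%, as stated. The design arithmetic is not in question.

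**2. How far a late start moves recorded PFS.** Take exponential PFS with a 4-month median: λ = ln 2/(4 × 30.44) = 0.00569 per day. Scans fall at d + 56k days from randomization, where d is the start delay. The mean scan-dated time is

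56 + d + 56·e^(−λd)·q/(1 − q), with q = e^(−56λ) = 0.727,

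so 56q/(1 − q) = 149.1 days. The change from d = 0 is d − 149.1(1 − e^(−λd)):

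- d = 3.5: about 0.6 days
- d = 7: 7 − 149.1 × 0.0391 = about 1.2 days
- d = 10: about 1.7 days

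The mean moves little, because some patients who progress during the shift are caught at the delayed scan and not 8 weeks later. Any effect on the test comes from the ordering of clustered event times.

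**3. False-positive rate under no treatment effect, nominal 0.10.** The documents give no delays by arm, so every delay here is an assumption. Randomization and registration are treated as the same day.

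*Model 1*: 76 per arm, 4-month median in both arms, 18 months' accrual, analysis at 24 months, 56-day scans with jitter limited to ±7 days, 10% of events dated exactly as deaths, exponential start delay capped at 30 days, unstratified logrank test, 4,000 trials per setting, Monte Carlo standard error about 0.005-0.006.

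| Mean delay, Arm A vs Arm B (days) | False-positive rate |
|---|---|
| 0 vs 0 | 0.10 |
| 7 vs 7 | 0.105 |
| 8 vs 7, 9 vs 7 | 0.11-0.12 |
| 10 vs 5 | 0.13 |
| 7 vs 3 | 0.14 |
| 3.5 vs 0 | 0.16 |
| 7 vs 0 | 0.18-0.19 |
| 7 vs 0, scans anchored to randomization | 0.10 |

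*Model 2*: start delays spread over only 9 days in each arm, all progression dated at scans, data cut at 125 events, 3,000-6,000 trials per setting. With equal delays the rate is 0.094-0.106. With Arm A later by 1, 3 or 7 days it is 0.116, 0.15 and 0.21 (mean HR 0.98, 0.96, 0.91). These are higher than Model 1 for a similar difference, because tightly spread start times keep the scan clusters sharp. The effect is not monotone: 0.25 at 14 days, 0.23 at 21, and 0.15 for 30 versus 0. If Arm A cycles ran longer by an assumed 0.5, 1 or 2 days each, the rate would be 0.15, 0.17 and 0.21.

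**4. The other direction (Model 2).** With Arm B later by 7 days, the false-positive rate is 0.044. Under the design effect the HR moves from 0.66 to 0.71 and power falls to about 72%, against 83% with equal delays.

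**5. Scans anchored to randomization (Model 2).** The false-positive rate is 0.095 with mean HR 1.00. Under the design effect, power is 82% and HR 0.66.

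**6. The optional switch after cycle 12 (Model 1).** If only Arm A takes it up, the rate is 0.104.

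**The case against.** The strongest objection is that nothing in the documents shows a delay that differs by arm. The visible causes of delay are shared: the pre-treatment biopsy after registration at external sites, confirmation of tissue, and neratinib supply. Both arms have the same Day 1 visit each cycle. Fulvestrant is an ordinary commercial product, Section 5.1 sets no order of administration, and the ±3-day window means Cycle 1 need not wait for it. This stands. It is why the point is a precaution.

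Other limits also stand. The 30 days is an outer bound for external sites, against a recommended 7 business days. Section 4.1 sends treatment delays to the Overall PI, and Section 11.1.3 restricts them indirectly. Neratinib holds do not move cycles, and neratinib may continue while fulvestrant is held. What remains open is the visit windows, late starts for other reasons, and fulvestrant holds.

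The simulations also give untreated waiting time the same hazard as treated time. If the hazard before first dose were 1.5, 2 or 3 times higher (an assumption), the 7-versus-0 rate would fall to 0.158, 0.143 or 0.098, and the 10-versus-5 rate to 0.119, 0.105 or 0.088.

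A reader might infer that each day of later start adds a day to recorded PFS. Step 2 shows that it does not. A reader might also suppose that injection visits set Arm A's cycle dates; no section says so.

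**Conclusion.** The two clocks have different anchors, and that is a fact of the text. Bias follows only if start times or cycle lengths differ systematically between arms. A reader might go further and conclude that the PFS comparison is biased towards the combination. The documents do not support that: they give no delay by arm, and equal delays leave the test at its nominal level.

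The supportable conclusion is one of sensitivity. A difference of 1-2 days on top of a shared 7-day delay takes the error rate from 0.10 to about 0.11-0.12, and 4-5 days to 0.13-0.14. Rates of 0.16-0.21 need Arm B to have little or no delay. All of this rests on assumed delays, exponential PFS, an unstratified test and equal hazard before and after first dose. The optional change of interval after cycle 12 is immaterial by comparison. The point merits a cheap improvement and does not invalidate the design.

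**What to change.** - In Section 11.1, Table 7 and footnote D, schedule tumour evaluations every 8 weeks (±7 days) from the date of randomization in both arms, regardless of first-dose date, cycle delays or drug holds.
- Place the later change to 12-weekly scans at one fixed time from randomization for all patients, for example week 48, which corresponds to 12 cycles of 28 days. This is a minor tidy-up.
- In Section 11.1.6, use randomization as the only PFS origin and drop the alternative of registration.
- Report time to first dose and time to each scan by arm, so that any difference is visible.

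The cost is wording. Sample size, event count and the stated 82.3% power do not change. The downside is that some scans will fall slightly before two full cycles are complete, and late starters will have had less drug exposure at the first scan.
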